## STUDY PROTOCOL AND STATISTICAL ANALYSIS PLAN

### 1. Study design

This randomized clinical trial involved patients with burning mouth seen at the Stomatology Service of the Department of Dentistry, Federal University of Rio Grande do Norte (UFRN), Natal-RN, Brazil, from April 2021 to February 2022. The study was approved by the Ethics Committee of UFRN (Approval number 4.066.032) and was conducted in accordance with the Declaration of Helsinki. This clinical trial followed the Consort Statement (<http://www.consort-statement.org>) and was registered at clinicaltrials.gov (Number: NCT05816200).

### 2. Participants

Patients older than 18 years who had a burning or dysesthetic sensation in the oral mucosa that recurred daily for more than 2 hours per day for more than 3 months, in the absence of clinically evident causal lesions [4], were included in the study. We also included patients with hyposalivation or any systemic alteration that could be related to a burning sensation in the oral mucosa but who did not have clinical alterations in the oral mucosa such as erosive lichen planus, geographic tongue, infections, allergic reactions, trauma, or injuries caused by physical or chemical agents. Patients who did not comply with the treatment protocol of the study were excluded from the sample.

Before the beginning of treatment, clinical and sociodemographic data of the patients were collected and blood tests were requested (complete blood count, fasting blood glucose, total cholesterol and fractions, triglycerides, ferritin, vitamin B12, folic acid, zinc, thyroxine, triiodothyronine, and antinuclear antibodies).

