### 3. Interventions

In the study group, a portable TENS 7000 device (Roscoe Medical, Middleburg Heights, OH, USA) was used for stimulation. The device was calibrated for a frequency of 50 Hz and its intensity was modulated according to the patient's comfort (pulse amplitude of 1-4). Each session lasted 25 minutes. The self-adhesive electrodes were connected to the channels of the device and **attached to the patient's skin** of both facial sides next of the major salivary glands (parotid and submandibular glands), passing through the mandibular branch of the trigeminal

nerve as shown in figure 1. The patients were submitted to the respective treatment protocol once a week for eight consecutive weeks, totaling 8 treatment sessions.

In the control group, photobiomodulation was applied using a laser whose parameters are represented in table 1. During laser application, the patients and the clinician wore the protective glasses (figure 2).

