#### 4. Outcomes

Pain/burning was the primary outcome and was measured on a visual analogue scale (VAS; 0-10 cm). The patients were asked to choose a number from 0 to 10 on the scale to describe the level of intensity of their symptoms.

Changes in unstimulated salivary flow, xerostomia, and dysgeusia were the secondary outcomes. Saliva was collected as described by Navazesh and Kumar [26] and patients with an unstimulated salivary flow rate  $< 0.1$  ml/min were classified as having hyposalivation.

Information on xerostomia was collected according to the method of Murray Thomson et al. (2006) using a standard question and the Xerostomia Inventory (XI). Patients answered the following question: "How often does your mouth feel dry?" (response options: "never", "occasionally", "frequently", "always"). On each occasion, those who gave either of the latter two responses were categorised as xerostomic. The XI was used to obtain information on the severity of xerostomia symptoms, being an 11-item summated rating scale which combines the responses to 11 individual items into a single continuous scale score which represents the severity of chronic xerostomia, and higher scores represent more severe symptoms. The patients were asked to choose one of five responses ("never", scoring 1; "hardly ever", 2; "occasionally", 3; "fairly often", 4 and "very often", 5) to the following statements referring to the previous 4 weeks: "my mouth feels dry"; "my lips feel dry"; "I get up at night to drink"; "my mouth feels dry when eating a meal"; "I sip liquids to aid in swallowing food"; "I suck sweets or cough lollies to relieve dry mouth"; "my throat feels dry"; "the skin of my face feels dry"; "my eyes feel dry"; "my lips feel dry" and "the inside of my nose feels dry". Each individual's responses were scored and summed to give a single XI score.

Dysgeusia was analyzed using an adaptation of the method proposed by Muller et al. [28], in which the four basic tastes at four different concentrations are tested. Urea was used as bitter taste as proposed by Henn et al. [29] (sucrose solution: 0.4 g/mL, 0.2 g/mL, 0.1 g/mL, 0.005 g/mL; sodium chloride: 0.25 g/mL, 0.1 g/mL, 0.04 g/mL, 0.016 g/mL; citric acid: 0.3 g/mL, 0.165 g/mL, 0.09 g/mL, 0.05 g/mL; urea: 0.005 g/mL, 0.04 g/mL, 0.02 g/mL, 0.01 g/mL). Filter paper strips were impregnated with the test solutions as proposed by Kettenmann et al.

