## 5. Sample size

The sample size was calculated according to Sikora et al. [31] who compared the efficacy of PBM to a placebo group (laser off). In that study, the mean and standard deviation (SD) of the VAS score in the placebo group at the end of treatment was  $2.417 \pm 2.918$ . Considering that acceptable improvement in the PBM group would be at least 10% after the intervention, we obtained an effect value ( $E$ ) = 2.17. The sample size was then calculated using a t-test for comparing the means of continuous variables, whose standardized effect size was 0.70 assuming a one-sided alpha error of 0.05 and a beta error of 0.20, resulting in 28 patients divided into two intervention groups.

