## 6. Randomization

After sample size calculation and selection of the sample according to the inclusion criteria, the patients were randomized to one of the two treatments (TENS or PBM) using an allocation software (<https://www.graphpad.com/quickcalcs/randomize1/>). This program did not randomly choose a treatment for each patient but randomly shuffled a defined number of patients among a defined number of treatment slots.

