## 8. Statistical analysis

All data were analyzed using the Statistical Package for the Social Sciences 25.0 (SPSS). First, the collected data were submitted to descriptive analysis. Fisher's exact test was then used to determine whether statistically significant differences in systemic alterations, psychiatric disorders and medication use exist at T0 between the TENS and PBM groups.

The quantitative data (VAS score and unstimulated salivary flow) were analyzed using the Kolmogorov-Smirnov normality test to assess if the data are normally distributed, which

was confirmed based on the mean error. Two-factor ANOVA was used to analyze intergroup (TENS and PBM) and intragroup (repeated measures at T0, T1, T2 and T3) differences in mean VAS scores and unstimulated salivary flow. For this purpose, the assumptions of sphericity were tested using the Mauchly test. The post-test of intergroup and intragroup interactions was carried out based on Bonferroni corrections, as well as using the trend test of the interaction between time and intervention. A level of statistical significance of 95% was adopted for all tests.

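### Mixed entry with no stratification or adjustment: with about 14 per arm, chance imbalance in hyposalivation or systemic status could distort this trial's estimate, and the T0 Fisher test is not an adequate safeguard

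*Combined protocol and SAP*

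**What the plan says.** All references are to the combined protocol and SAP.

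- **Entry (section 2, Participants).** Besides patients whose burning has no evident causal lesion, the plan adds a second kind: "We also included patients with hyposalivation or any systemic alteration that could be related to a burning sensation in the oral mucosa". The size of this subset is not given.
- **Status is known before treatment.** Section 2 says: "Before the beginning of treatment, clinical and sociodemographic data of the patients were collected and blood tests were requested". Section 4 (Outcomes) collects unstimulated flow at T0, and patients below 0.1 ml/min are "classified as having hyposalivation". Unstimulated flow is also a secondary outcome.
- **Allocation (section 6, Randomization).** The software "randomly shuffled a defined number of patients among a defined number of treatment slots". No stratification factor is named.
- **Analysis (section 8, Statistical analysis).** VAS and flow are each analysed by a two-factor ANOVA: group, and time at T0, T1, T2 and T3. There is no covariate, and T0 is one of the response levels. At baseline, Fisher's test is used to see whether "statistically significant differences in systemic alterations, psychiatric disorders and medication use exist at T0" between the arms. Hyposalivation is not on that list, and nothing is said about what follows from a significant or non-significant result.

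**The concern.** The plan itself treats hyposalivation and systemic alterations as possibly related to burning, and section 3 (Interventions) places the TENS electrodes beside the major salivary glands. It is therefore plausible that these patients differ from the rest in VAS or in flow.

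For flow the link needs no outside evidence: hyposalivation at T0 is the baseline value of that outcome, cut at 0.1 ml/min.

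In a trial this small, one arm can easily receive noticeably more such patients by chance. The plan neither limits this at allocation nor corrects for it in the model, and a non-significant Fisher result could be taken as evidence that the arms are comparable.

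**Working it through.** **Inputs from the documents.** Section 5 gives a total of 28: "resulting in 28 patients divided into two intervention groups". It also gives an SD of 2.918 for VAS, from the placebo arm of the cited study. The allocation ratio is not stated.

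**Assumptions.** 14 patients per arm; K of the 28 in the subset, with K from 3 to 14; the subset differs from the rest by 1 to 2 VAS points.

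**The plan's own figure.** The total of 28 does not reproduce. With "one-sided alpha error of 0.05 and a beta error of 0.20" and an effect size of 0.70, n per arm = 2(1.645 + 0.842)² / 0.70² = 25.2, so 26 per arm and 52 in total. That is a separate issue; 28 is used here only to set the arm sizes.

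**Step 1: chance of a gap.** If X of the K subset patients fall in one arm, X is hypergeometric (28, K, 14) and the gap between arms is |2X − K|. For K = 14 there are 40,116,600 equally likely allocations. The 7 v 7 and 8 v 6 splits account for 11,778,624 + 2 × 9,018,009 = 29,814,642. The chance of a gap of 4 or more is therefore 10,301,958 / 40,116,600 = 25.68%. Other values:

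| K | P(gap ≥ 4) | K | P(gap ≥ 4) |
|---|---|---|---|
| 3 | 0% | 9 | 10.32% |
| 4 | 9.78% | 10 | 23.65% |
| 5 | 4.07% | 11 | 12.01% |
| 6 | 16.47% | 12 | 25.19% |
| 7 | 7.68% | 13 | 12.83% |
| 8 | 20.87% | 14 | 25.68% |

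Odd K allows only odd gaps, so 4 or more then means 5 or more. The range is 10% to 26% for K = 8 to 14, and 0% to 16% for K = 3 to 7.

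**Step 2: what Fisher's test would show.** Two-sided p with 14 per arm: 7 v 3, 0.24; 8 v 4, 0.25; 9 v 5, 0.26; 10 v 4, 0.057. A gap of 4/14 = 29 percentage points passes easily, and in the 10 v 4 split a gap of 6/14 = 43 points still passes.

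**Step 3: shift in the VAS comparison.** Shift = (gap / 14) × subset difference. For a gap of 4: 4/14 × 1 = 0.29 and 4/14 × 2 = 0.57 points, or 0.10 and 0.20 SD (dividing by 2.918). For a subset difference of 0.5 points it is 0.14.

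**Step 4: effect of adjustment.** Simulation of a comparison at one time point: 14 per arm, K = 14, total SD 2.918, two-sided 5%, 15,000 runs per setting, with and without the subset indicator in the model.

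| | Unadjusted | Adjusted |
|---|---|---|
| Mean error over all allocations, no true effect | 0.01 or less | 0.01 or less |
| Type I error over all allocations | about 5% | about 5% |
| Mean spurious difference, gap ≥ 4 against one arm, subset effect 2 | 0.69 | 0.05 |
| False positives given a gap ≥ 4, subset effect 2 | 7.7% | 5.0% |
| False positives given a gap ≥ 4, subset effect 1 | 6.3% | 5.5% |
| Power at d = 0.70, subset effect 2 | 42% | 46% |
| Power at d = 0.70, subset effect 1 | 43% | 42% |

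The 0.69 exceeds the 0.57 of step 3 because it averages over gaps of 4 and more. The exact mean gap given 4 or more is 4.50, so the expected shift is 4.50/14 × 2 = 0.64. The excess of about 0.05 in both columns is simulation noise.

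**The case against.** A reader might infer that the TENS-PBM comparison is biased. The documents do not support that. Chance imbalance after a valid shuffle leaves the estimate unbiased on average, and type I error stays near 5% (step 4). The cost is a misleading estimate in an unlucky allocation, plus some lost precision. This objection stands.

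A reader might also infer that the analysis ignores the split altogether. It does not: systemic alterations are tested at T0, and flow is compared between arms across T0 to T3 with Bonferroni post-tests. What remains is that hyposalivation as such is not on the Fisher list, that the test cannot flag plausible gaps at this size, and that no result changes the model.

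Third, the planned ANOVA includes a group-by-time interaction, in which a subset difference that is constant over time cancels. That is correct, so the shift in step 3 applies to a post-treatment comparison, to the group main effect, or to a subset difference in change. The interaction does not remove a difference in how far low-flow patients can change, and the group main effect, averaged over T0 to T3, carries any baseline gap.

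Finally, section 2 says only that these conditions could be related to burning. It shows neither that they predict VAS nor that they modify the TENS effect. This stands too: for VAS the prognostic effect is an assumption, and effect modification is only a conjecture that 28 patients could hardly test.

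**Conclusion.** The point holds as a matter of precision and of accuracy given the allocation obtained, not as a flaw in validity. Entry is mixed by design, and neither the shuffle nor the model accounts for it. The baseline test is not an adequate safeguard.

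The size depends on figures the documents do not give: subset prevalence, the VAS difference between subset and rest, and a 1:1 ratio. Under the stated assumptions a gap of 4 or more is far from rare when 8 or more of the 28 are in the subset, and it moves the VAS difference by 0.10 to 0.20 SD. With few subset patients, or a VAS difference of 1 point or less, the matter is small. The case is firmest for salivary flow, where the omitted factor is the outcome's own baseline.

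**What to change.** In section 8:

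1. **Salivary flow.** Take T0 out of the response and compare the arms at T1 to T3 with T0 flow as a covariate. T0 flow cannot be both a response level and a covariate in the same model.
2. **VAS.** Analyse T1 to T3 adjusted for T0 VAS and T0 unstimulated flow (or the indicator for flow below 0.1 ml/min), with covariate-by-time terms.
3. **Reporting.** Give the adjusted TENS-PBM difference. Replace the T0 Fisher test with a descriptive baseline table by arm that includes hyposalivation and systemic alterations.

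**Cost.** No new patients or measurements. For VAS with 28 patients, two covariates take the between-patient error from 28 − 2 = 26 to 24 degrees of freedom. Their time terms take the within-patient error over three visits from 26 × 2 = 52 to 24 × 2 = 48. If T0 flow is not prognostic for VAS, it adds little there. Systemic alterations are described in the table but not adjusted for.

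Section 1 dates the study from April 2021 to February 2022, so a separate shuffle within strata of T0 flow is advice for a future trial only. For the same reason, if the adjusted analysis is added now, it should be labelled as an addition and shown beside the planned ANOVA.

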[30]. The strips were placed in the center of the tongue and the patient was asked to identify the taste. The 10th percentile was used to define the presence or absence of dysgeusia.

The primary and secondary outcomes were collected at baseline (T0), after the 4th treatment session (T1), after the 8th treatment session (T2), and 30 days after the end of treatment (T3).

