## 7. Blinding

Blinding was not possible since the devices used for the interventions performed in the study and control groups were different.

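### Patients who do not comply are dropped after randomisation and no analysis of all randomised patients is planned, so the TENS versus PBM comparison can be biased by an unknown amount

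*Combined protocol and SAP*

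**What the plan says.** The exclusion closes the eligibility paragraph of section 2: "Patients who did not comply with the treatment protocol of the study were excluded from the sample". No minimum number of sessions or other definition of compliance is given.

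Section 6 places allocation after eligibility: "After sample size calculation and selection of the sample according to the inclusion criteria, the patients were randomized to one of the two treatments". Section 3 gives the course to be complied with: "once a week for eight consecutive weeks, totaling 8 treatment sessions".

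Section 4 makes the 0-10 VAS the primary outcome. It ties T1 and T2 to the fourth and eighth sessions, and T3 to 30 days after treatment ends.

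Section 7 states that the trial is open: "Blinding was not possible since the devices used for the interventions performed in the study and control groups were different".

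Section 8 describes the analysis: "Two-factor ANOVA was used to analyze intergroup (TENS and PBM) and intragroup (repeated measures at T0, T1, T2 and T3) differences". It names no analysis set, missing-data rule or sensitivity analysis. Section 5 ends at 28 patients with no stated allowance for losses. Section 1 says the trial followed the CONSORT Statement, but nothing in the document commits to analysing everyone who was randomised.

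**The concern.** A patient can fail to comply with an assigned eight-session course only after the assignment. Although it sits among the eligibility criteria, the sentence therefore works as a post-randomisation exclusion. Once it is applied, the groups compared are those who stayed with TENS and those who stayed with PBM, and randomisation no longer guarantees that they are alike.

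This design is exposed to that problem. Patients and staff know the treatment, the outcome is the patient's own rating, and nobody has said in advance what counts as non-compliance. Losing patients who got little relief flatters an arm; losing patients who felt better and stopped attending does the opposite. With 28 patients, and 14 per arm if allocation is equal (the ratio is not stated), one exclusion removes 1/14 = 7% of an arm.

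Two further features add to the difficulty. A patient who misses sessions has no clearly defined T1, T2 or T3. In its standard form, a repeated-measures ANOVA also needs a complete T0-T3 record; that follows from the method and is not a rule the plan states.

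**Working it through.** **Timing.** Section 2 does not say when the exclusion is applied. Eligibility is settled, then patients are allocated (section 6), then they receive the course belonging to their arm over eight weeks (section 3). Compliance with that course is not observable before allocation. This is an inference, but the document allows no other order.

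**Inputs.** From section 5: SD 2.918, mean 2.417, total 28, one-sided alpha 0.05, beta 0.20, and a standardised effect ("whose standardized effect size was 0.70"). Assumed: equal arms of 14, the number excluded (k), and how strongly exclusion depends on the score. The document gives no counts or scores for excluded patients.

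**The plan's own figure.** Per arm, n = 2(1.645 + 0.842)² / 0.70² = 25.2, rounded up to 26, or 52 in total. The stated 28 is not reproduced. That is a separate problem and this point does not depend on it. It does mean that with 14 per arm the one-sided power of the t-test is 56%, falling to 54%, 51% and 48% if 1, 2 or 3 patients per arm are excluded.

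**Scale.** The planned effect is 0.70 × 2.918 = 2.04 points. Section 5 also prints an effect value of 2.17, which would be 2.17/2.918 = 0.74 SD; using it changes little below.

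**Arithmetic of one exclusion.** If k of 14 patients are dropped from one arm and their mean VAS is g points worse than that of the compliers, the arm mean moves by (k/14) × g.
- k = 1, g = 1: 0.07 points (3% of 2.04).
- k = 2, g = 2.918 (1 SD): 0.42 points (20%).
- k = 4, g = 4: 1.14 points (56%).

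**Simulation.** Two normal arms of 14, no true difference, k patients removed from one arm according to a latent score with correlation ρ to the end-of-treatment VAS, two-sample t-test at two-sided 5%, 200,000 trials. A negative shift favours the arm with exclusions.

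| ρ | Shift in points, k = 1 / 2 / 3 | Two-sided error, k = 1 / 2 / 3 |
|---|---|---|
| 0 | 0.00 / 0.00 / 0.00 | 5.1% / 5.0% / 5.1% |
| 0.3 | −0.11 / −0.21 / −0.31 | 5.2% / 5.5% / 5.8% |
| 0.5 | −0.19 / −0.35 / −0.51 | 5.6% / 6.2% / 7.3% |
| 1 (worst scorers leave) | −0.38 / −0.71 / −1.01 | 7.2% / 11.0% / 16.0% |

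The shift is proportional to ρ, which checks the table: 0.5 × 0.38 = 0.19 and 0.3 × 0.71 = 0.21.

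**Variations.**
- The same number removed from both arms, ρ = 1: shift 0.00, but error 7.0% / 8.6% / 9.9%.
- Bounded 0-10 scale with the same mean and SD (10 × beta(0.279, 0.874)), ρ = 1: −0.46 / −0.86 / −1.21 if the worst scorers leave, +0.19 / +0.40 / +0.65 if the best leave.
- Change from T0, with within-patient correlation r (assumed): the shift is multiplied by 1 − r. The extreme case becomes −0.19 / −0.35 / −0.51 at r = 0.5 and −0.12 / −0.22 / −0.30 at r = 0.7. At ρ of 0.3 to 0.5 it runs from 0.3 × 0.38 × 0.3 = 0.03 to 0.5 × 1.01 × 0.5 = 0.25 points.

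**What can be recovered (ρ = 1).** If T2 is collected from every randomised patient, the shift is 0.00. If T2 was not collected but T0 and T1 are kept in a likelihood analysis, −0.26 / −0.50 / −0.71 remains at r = 0.5 and −0.18 / −0.33 / −0.47 at r = 0.7.

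**The case against.** The strongest reply is that no harm is shown. The document reports no exclusions; if there were none, the compliers are the randomised patients and the bias is zero. That stands, and it is why the conclusion is that the comparison can be biased, not that it is.

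The figures are also modest away from the extremes. At correlations of 0.3 to 0.5 the error rate stays between 5.2% and 7.3% even with all exclusions in one arm, and similar exclusions in both arms give about no net shift. The illustration uses one visit and a t-test, whereas the plan is a repeated-measures ANOVA with a time-by-treatment interaction; on change from T0 the shifts are smaller still. All of this stands and limits what can be said about size.

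Two other replies carry less weight. That section 2 gives no timing is true, but compliance with an assigned course cannot precede the assignment. That the trial followed CONSORT is a general statement, and it does not cancel a specific rule removing patients from the sample.

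On the remedy, the reply is partly right. The dates in section 1 (April 2021 to February 2022) suggest data collection is over, so re-timing visits may be impossible, and the mixed model is secondary to the choice of analysis set.

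**Conclusion.** The point holds, and the plan is wrong as written. It contains an explicit rule removing randomised patients from an unblinded comparison of a self-reported outcome, and nothing elsewhere restores them.

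Neither the size nor the direction of the bias can be determined from the document. Under the assumptions above, the single-visit shift ranges from 0 to about −1.01 points (−1.21 on the bounded scale) when worse scorers leave one arm, and up to +0.65 when the best scorers leave. The largest values are 1.01/2.04 = 0.50 and 1.21/2.04 = 0.59 of the planned effect and need selection exactly on the final score in one arm. Moderate dependence gives 0.11 to 0.51 points, or 0.03 to 0.25 on change from T0.

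It must be fixed because the rule gives up the protection of randomisation for the primary comparison and leaves a reader unable to tell where in that range the trial lies. The case does not rest on the extreme figures.

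**What to change.** Essential changes:
1. Delete the exclusion sentence from section 2.
2. State in section 8 that the primary analysis includes all randomised patients in the group allocated, with every VAS value already collected, whether or not they completed the sessions.
3. Report exclusions and missing visits by arm, with reasons.
4. Add one sensitivity analysis that sets missing scores to unfavourable values (the patient's own T0 score, then the worst observed score), first in one arm, then in the other, then in both.

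Secondary changes:
- Use a linear mixed model on all available visits (SPSS MIXED, in the package already named) in place of an ANOVA that needs complete records. It does not fully correct for scores missing because of their value, so item 4 is still needed.
- Define non-compliance for analysis purposes, for example as a stated minimum number of sessions attended, and keep the compliers-only result as a sensitivity analysis.
- Only if follow-up is still possible, time assessments by calendar (week 4, week 8 and 30 days after week 8) so that patients who miss sessions have defined visits. This moves assessment dates and leaves treatment unchanged, but T1 and T2 would then mean time elapsed and not sessions received; the plan should say so.

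The cost is wording and a modest reanalysis. The effect estimate may be slightly diluted by non-compliance. Scores never collected may be unrecoverable; in that case the retained visits, the counts by arm and the sensitivity analysis are what remain.
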